10.5.2 Adverse Events

AEs will be recorded during the study period from Screening Visit to the completion of the End-of-Study Visit.

SAEs will be recorded during the study period from Screening Visit to the completion of the End-of-Study Visit or up to 30 days after last dose of IMP administered in the study, whichever occurs later.

AEs will be coded using the Medical Dictionary for Regulatory Activities (MedDRA) version 17.1. The severity of AEs will be graded using the NCI CTCAE version 4.0 [2]. For further information of definitions and reporting of AEs and SAEs, see *Section 11* below.

Medical conditions or diseases present before Screening Visit are only considered AEs if they worsen after Screening Visit. Non-serious events occurring after signing the Informed Consent Form (ICF) but before any assessments made at the Screening Visit are recorded as Medical History in the eCRF.

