Minimal, local or noninvasive intervention indicated OR limiting age-appropriate instrumental Activities of Daily Living (ADL). (Instrumental ADL refer to preparing meals, shopping for groceries or clothes, using the telephone, managing money, etc.)

Grade 3 (Severe or medically significant but not immediately life-threatening)

Hospitalization or prolongation of hospitalization indicated OR disabling OR limiting self-care ADL. (Self-care ADL refer to bathing, dressing and undressing, feeding self, using the toilet, taking medications, and not bedridden.)

Grade 4 (Life-threatening consequences)

Urgent intervention indicated.

Grade 5 (Death related to AE)

If an AE changes in severity, the worst severity should be reported.

Causality

Causality will be assessed as:

Probable

A clinical event, including laboratory test abnormality, with a reasonable time sequence to administration of the IMP, unlikely to be attributed to concurrent disease or other drugs or chemicals, and which follows a clinically reasonable response on withdrawal (dechallenge). Rechallenge information is not required to fulfil this definition.

Possible

A clinical event, including laboratory test abnormality, with a reasonable time sequence to administration of the IMP, but which could also be explained by concurrent disease or other drugs or chemicals. Information on IMP withdrawal may be lacking or unclear.

Unlikely

A clinical event, including laboratory test abnormality, with a temporal relationship to IMP administration which makes a causal relationship improbable, and in which other drugs, chemicals or underlying disease provide plausible explanations.

Follow-up of Patients after Adverse Events

Any AE that is ongoing when the patient is withdrawn from the study should be followed up until the AE is resolved or the Investigator decides that the AE is stable and needs no further follow-up.

Abnormal Laboratory Values/Vital Signs

The reporting of abnormalities as both laboratory/vital signs findings and AEs should be avoided.

An asymptomatic abnormal laboratory/vital sign finding should only be reported as an AE if it is clinically significant, if it fulfils the criteria for an SAE or if it causes the patient to discontinue the study.

If an abnormal laboratory/vital sign value is associated with clinical signs and symptoms, the sign/symptom should be reported as an AE and the associated laboratory/vital sign result should be considered additional information.

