6.6 Handling of Dropouts and Missing Data

Primary and secondary efficacy endpoint

The primary and secondary efficacy endpoint analysis will be conducted on available data (observed cases). Missing data due to loss of follow-up and rules for censoring will be done as described in each corresponding section.

Handling of incomplete dates

Incomplete (partial or missing) dates will be presented in data listings as provided on the eCRF. However, for use in calculations (e.g. to calculate the duration of an AE or medication use) dates will be estimated as follows.

For partial start-dates

- If the year is unknown, then the date will not be imputed and will be assigned a missing value
- If the month is unknown, then:
 - If the year matches the year of the first dose date, then impute the month and day of the first dose date
 - Otherwise, assign 'January'
- If the day is unknown, then:
 - If the month and year match the month and year of the first dose date, then impute the day of the first dose date.
 - Otherwise, assign 'January'.

For partial end-dates,

- If the year is unknown, then the date will not be imputed and will be assigned a missing value.
- If the month is unknown, then assign 'December'.
- If the day is unknown, then assign the last day of the month

If the above rules for end-dates result in a date after the patient was ended the study, then the end date will be replaced with the patient's date of completion/withdrawal. Furthermore, should the above rules not result in the most conservative date (as described below), then the imputed value may be replaced by a date that will lead to a more conservative analysis.

After implementing the rules above, to determine whether AEs with incomplete start or stop dates are pre-treatment or treatment-emergent the following strategy will be used:

- If the start date and stop date are both missing, the most conservative approach is taken and the AE is considered to be treatment-emergent
- If the start date is missing but the stop date is not missing and is on or after the day of first study drug administration but before or on the Week 12 visit date then the most conservative approach is taken and the AE is considered to be treatment-emergent;
- If the start date is missing but the stop date is not missing and is before the day of first study drug administration then the AE is considered to be pre-treatment.

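### The partial-date rules in SAP 6.6 ignore the event's other, known date, so an imputed AE start can fall after its stop and a capped end before its start

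*SAP*

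**What the plan says.** SAP 6.6 (Handling of incomplete dates) says that, "for use in calculations (e.g. to calculate the duration of an AE or medication use) dates will be estimated as follows". For a start with the month unknown: "If the year matches the year of the first dose date, then impute the month and day of the first dose date". For a start with only the day unknown: "If the month and year match the month and year of the first dose date, then impute the day of the first dose date". Neither rule refers to the stop date of the event.

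A partial end goes to the end of the recorded month, or to December if the month is unknown, and is then capped: "If the above rules for end-dates result in a date after the patient was ended the study, then the end date will be replaced" by the date of completion or withdrawal. The cap does not refer to the start date. The next sentence adds that, where the result is not the most conservative, "the imputed value may be replaced by a date that will lead to a more conservative analysis".

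Only after these steps does SAP 6.6 decide whether an AE is pre-treatment or treatment-emergent. The one branch that uses a known stop before first dose is worded for an AE whose start is missing.

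On collection, Protocol 10.5.2 records AEs from Screening, so before any dose. For serious events it says "SAEs will be recorded during the study period from Screening Visit to the completion of the End-of-Study Visit or up to 30 days" after the last dose of IMP, whichever is later. Protocol 11.2 also requires 30 days of SAE collection in treated patients who withdraw early.

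**The concern.** Nothing in SAP 6.6 requires the start to be on or before the stop. AEs that begin and resolve between Screening and first dose are expected, because the first vaccination may come up to 28 days after Screening (Protocol 7.2.1.2). SAEs that begin after the End-of-Study Visit or withdrawal are also expected, because the protocol collects them. These are the events on which the two rules can fail.

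At stake is the credibility of some safety outputs. An AE that was over before first dose could be shown as treatment-emergent and be absent from the pre-treatment summary, and some listed durations would be negative. Safety is a secondary objective, and programmers will apply the rules as written.

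**Working it through.** The SAP states no figure to reproduce, so the check applies its rules literally to illustrative dates.

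Assumptions, because the SAP gives no definition:
- Duration = stop − start + 1 day, as in the SAP's own time-to-event derivations (6.3.5, 6.3.6).
- Treatment-emergent means a start on or after first dose, the boundary that the status rules use.
- First dose is the first dose of any IMP.
- Completion/withdrawal is the End-of-Study Visit or withdrawal date.

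1. **Day unknown.** First dose 20 March, start recorded as March, stop 9 March. The month matches, so the start becomes 20 March, 11 days after the stop. Duration = 9 − 20 + 1 = −10 days. Status: treatment-emergent.
2. **Month unknown.** First dose 20 May 2017, start recorded as 2017, stop 28 April 2017. The year matches, so the start becomes 20 May, 22 days after the stop. Duration = −22 + 1 = −21 days. Status: treatment-emergent.
3. **Start wholly missing.** As case 1, but with no start at all. Nothing is imputed, and the missing-start branch with a stop before first dose applies. Status: pre-treatment, which is correct. The same event with more information recorded is classified worse.
4. **End cap.** Exit 10 March 2018, SAE start 25 March 2018.
   - End recorded as March: month-end 31 March is capped to 10 March. Duration = 10 − 25 + 1 = −14 days, against 31 − 25 + 1 = 7 without the cap.
   - End recorded as April: 30 April is capped to 10 March, again −14 days, against 36 + 1 = 37 without the cap.
   - The start is known and after first dose, so the status does not change.

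**Reach of the start rule in the Intuvax arm.** The enumeration took Screening on every day of 2017, first vaccination on Day 2 to 28, and every start/stop pair that resolved before vaccination, with equal weights (an assumption). Where the month did not match, the first of the recorded month was used, because the SAP's fallback for an unknown day names a month, not a day.
- Day unknown: 719,838 / 1,333,710 = 54% get a start after their own stop.
- Month unknown: 1,282,554 / 1,333,710 = 96%.

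These shares apply only to AEs that resolved before first dose and have a partial start. They show how far the rule reaches among such records and do not forecast how many there will be.

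**Where the result appears.** Treatment-emergent status is a flag in the AE listing (SAP 6.3.10). Pre-treatment events have their own summary (SAP 6.3.10; Appendix 1 tables 14.3.1.10 and 14.3.1.11, listing 16.2.7.4). Durations may be shown in listings (SAP 6.3.3). The main AE summaries in SAP 6.3.10 are not restricted to treatment-emergent events.

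**The case against.** **The status rules may already cover this.** Their lead-in speaks of incomplete dates, and SAP 6.6 uses that word for partial and missing dates together. If 'missing' in the rules was meant to include partial starts, cases 1 and 2 return to pre-treatment. This stands as a possible reading, so the misclassification is not certain. It does not remove the start after the stop or the negative duration.

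**There is an override, and the data are reviewed.** The override is optional, sets no order between start and stop, and aims at the more conservative date. SAP 6.6 treats treatment-emergent as the conservative choice for AEs, so the override gives no reason to undo the error. SAP 6.2 provides edit checks, queries and a Pre-Analysis Review Form before database lock. These could catch an inverted pair, but a start in March with a stop on 9 March is consistent as recorded. The imputation creates the conflict, and no written rule resolves it.

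**The exit date may include the safety evaluation.** If completion/withdrawal meant the end of the 30-day evaluation, the end-cap problem would vanish. The SAP does not say so.

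Three stronger readings are tempting, and the documents do not support them:
- *Late SAEs lose their correct flag.* They do not. The cap moves only the end date.
- *AEs followed after withdrawal are inverted.* Protocol 11.2 says "Any AE that is ongoing when the patient is withdrawn from the study should be followed up until the AE is resolved". Such events began before exit, so the cap can shorten them but cannot place the end before the start.
- *Partial dates of death are pulled back to exit, which would change survival.* SAP 6.6 sends missing efficacy data and censoring to the section for each endpoint, which for OS is SAP 6.3.5. Protocol 11.3 keeps post-study survival information in the safety database, outside the clinical database. Nothing in the plan applies these AE and medication rules to deaths.

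**Conclusion.** The rules are wrong as written: followed literally, they give impossible date pairs in foreseeable situations. The start rule gives negative durations and, if an imputed partial start no longer counts as missing, moves resolved pre-dose AEs into treatment-emergent status. The end cap gives negative durations only, and only if completion/withdrawal means the End-of-Study Visit or withdrawal date.

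The consequence is small: one listing flag, the pre-treatment AE tables and listing, and listed durations. The main AE summaries and both primary survival endpoints are not affected. The documents do not say how many dates will be partial, so the number of affected records cannot be estimated. The reason to act is that the error is demonstrable and nearly free to remove before database lock.

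**What to change.** Add to SAP 6.6:

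*An imputed start date is the earlier of the rule date and the known stop date. The cap at completion/withdrawal is not applied when the event's start is after that date, and no imputed end date may be earlier than the start date. The status rules apply to partial as well as missing start dates, using the pre-treatment window defined for each arm in SAP 6.3.10.*

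Rechecking the cases: case 1 starts on 9 March and case 2 on 28 April 2017, each with a duration of 1 day and pre-treatment status. Case 4 ends on 31 March (7 days) or 30 April 2018 (37 days).

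The reference to arm-specific windows is needed. A blanket rule that any AE stopping before first dose is pre-treatment would conflict with SAP 6.3.10, where the window for unvaccinated patients closes at Nephrectomy. Their first IMP dose is sunitinib, five to eight weeks later, so surgical AEs that resolve in between would be labelled pre-treatment in the control arm only.

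The cost is a few lines of SAP text and a small programming change. No new data are needed.

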7.2.1.9 Extra Visits

Extra Visits are applicable for all patients if any symptoms need follow-up between planned visits.

TIMING:

The patient will be scheduled for a visit as soon as possible.

ACTIVITIES AND ASSESSMENTS:

- Concomitant Medication, *Section 10.4.4*
- Physical Examination, *Section 10.5.3*
- Vital Signs, *Section 10.5.4*

- Laboratory Safety Blood Assessments: Hematology and Clinical Chemistry. If the Extra Visit is scheduled after the Sun-Start Visit the assessments will also include GFR based on Creat, Gluc, TSH, and Thyroxine [free T4], *Section 10.5.5*
- Laboratory Safety Urine Assessments, *Section 10.5.5*
- ECOG performance status, *Section 10.2.3.1*
- AEs, *Section 11.2*
- Additional laboratory tests and other assessments as applicable to the discretion of the Investigator

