9.3 Selection of Doses in the Study

Intuvax

The Intuvax dose to be administered in this study consists of 10×10^6 viable and HLA class II expressing DCs. The outcome of Immunicum AB's first-in-man study of Intuvax in RCC

patients (Protocol No.: IM-101 and EudraCT No.: 2011-002039-25) in which doses of 5×10^6 , 10×10^6 , and 20×10^6 DCs have been administered formed the basis for the dose selection.

The same dose of Intuvax will be injected two (2) times with a 14 ± 3 day interval into the viable part of the renal primary tumor during the period while the patient is awaiting nephrectomy. The patients will receive the vaccine cells from the same batch (i.e. the same donor) at both administrations. A survival of between 24 and 48 hours is expected for the injected DCs after the first vaccination and a considerably reduced survival after the second injection. On the other hand, the second administration triggers the inherent immune response memory initiated by the first administration. A 14 days period between dosing is suggested to avoid administration of a second dose to a patient with an exhausted immune system. This time-window also reflects the time between diagnosis and nephrectomy in routine care.

The suggested dose is also supported by the pre-clinical program on Intuvax that has been performed by Immunicum AB consisting of four (4) studies in rat. In order to mimic the human situation vaccine cells derived from circulating monocytes were used in the proof-of-concept study (VP10-14), the pilot-toxicology study (VP10-17), the toxicology study (VP10-43), and the biodistribution study (AB11-01). The toxicology study VP10-43 did not reveal any major changes in general health status, vital signs and laboratory parameters.

Sunitinib

The sunitinib dose to be administered in this study is in accordance with the SmPC/USPI from start of treatment.

Duration of treatment

Intuvax

Two (2) injections of Intuvax will be administered with 14 ± 3 days interval followed by Nephrectomy in accordance with local routine at least 3 days after the second vaccination and maximum 63 days from Screening.

Sunitinib

Administration to be initiated five (5) to eight (8) weeks after nephrectomy for all patients. Treatment will continue until End-of-Study (78 ± 2 weeks after Screening) unless terminated due to unacceptable side-effects or other reasons. For post study treatment see *Section 9.9*.

Active control, dosage and mode of administration

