6.3.11 Other Safety Assessments

Vital Signs

For vital signs parameters (systolic and diastolic blood pressure, supine heart rate and temperature) summary statistics will be produced for observed values by visit. In addition, the difference from baseline to each visit at which they were assessed will be derived and presented.

Vital signs assessed at time points post vaccination will be summarised separately.

Clinical Laboratory Measurements

The laboratory categories are Hematology, Clinical Chemistry, Coagulation, Urine analysis and Pregnancy analysis.

For all laboratory parameters, summary statistics will be produced for observed values by visit. In addition, the difference from baseline to each visit at which they were assessed will be derived and presented. The number of abnormal (low and high) and clinically significant observations will be tabulated for each treatment group by visit. Abnormal values will be flagged in listings.

Shift tables that show the number of patients who changed from low, normal or high at baseline to low, normal or high at each post-baseline time of assessment will be presented.

Physical Examination

Physical examination results will be tabulated including number of subjects with normal, abnormal not clinically significant or clinically significant abnormalities by visit. Corresponding shift tables for changes from baseline will be presented, and all the results will be listed.

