If the date of first and/or last dose of study drug administration is missing then duration of exposure will be set to missing.

Handling of unscheduled visits

Descriptive summaries and by-visit analyses will be presented according to the planned (scheduled) visits, unless otherwise specified.

For patients withdrawing early, where discontinuation data is collected on the end-of-trial visit, the data will be reallocated to the visit nearest to withdrawal, if applicable.

Any data collected on unscheduled visits, will be reallocated to the visit nearest in time to the planned visits where the corresponding information is not already available. This will be done by allocating the unscheduled data within the visit windows by corresponding visit as listed below.

Vacc1	from screening to 28 days
Vacc2	+/- 3 days
	At least 3 days after Vacc2 Visit and within 63 days from Screening Visit for patients randomized to Intuvax followed by sunitinib. Within 63 days from Screening Visit for patients randomized to sunitinib only.
Nephrectomy Visit:	
Sun-Start Visit:	Five (5) to eight (8) weeks after Nephrectomy Visit
SFU[6W]:	6 weeks (± 7 days) after Sun-Start Visit
SFU[12W]:	12 weeks (± 7 days) after Sun-Start Visit
SFU[24W]:	24 weeks (± 7 days) after Sun-Start Visit
SFU[36W]:	36 weeks (± 7 days) after Sun-Start Visit
SFU[48W]:	48 weeks (± 7 days) after Sun-Start Visit
SFU[60W]:	60 weeks (± 7 days) after Sun-Start Visit
End of Study Visit:	78 \pm 2 weeks after Screening

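### SAP 6.6 can keep abnormal values from symptom-driven extra visits out of the by-visit laboratory, vital-sign and examination tables, and no worst-value summary is planned to catch them

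*SAP*

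**What the plan says.** SAP 6.6, under unscheduled visits, presents by-visit analyses at the planned visits. Data from unscheduled visits are to be "reallocated to the visit nearest in time to the planned visits where the corresponding information is not already available". The next sentence limits how: "This will be done by allocating the unscheduled data within the visit windows by corresponding visit as listed below". The list that follows repeats the protocol's visiting windows: Vacc1 up to day 28 from Screening; Vacc2 ±3 days; nephrectomy within 63 days of Screening (for the Intuvax arm also at least 3 days after Vacc2); Sun-Start; six follow-up visits at ±7 days; and End-of-Study at 78 ± 2 weeks.

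The main source of unscheduled data is Protocol 7.2.1.9: "Extra Visits are applicable for all patients if any symptoms need follow-up between planned visits". These visits collect haematology, clinical chemistry, urinalysis, vital signs, physical examination and ECOG status. After Sun-Start they add GFR, glucose and thyroid tests.

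On the output side, SAP 6.3.11 says: "The number of abnormal (low and high) and clinically significant observations will be tabulated for each treatment group by visit". Laboratory shift tables and examination results are also by visit. Vital signs get summary statistics and change from baseline by visit, without abnormality counts. Neither 6.3.11 nor Appendix 1 (14.3.4.3, 14.3.4.4, 14.3.6, 14.3.7) describes a worst-post-baseline or any-time summary. Entry 14.3.4.2 names other laboratory analyses without describing them.

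**The concern.** Extra visits are triggered by symptoms, so their results are more likely to be abnormal than routine ones. Two features of SAP 6.6 can keep those results out of the by-visit tables. One is the condition that the planned visit must be empty. The other is a set of windows written for scheduling visits, with long stretches between them. Clinically significant changes in laboratory tests and vital signs are part of a named secondary safety endpoint (Protocol 10.1), so what these tables leave out matters.

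A separate problem lies in the early windows. Blood samples at Vacc1 and nephrectomy are meant to be taken before the procedure (Protocol 7.2.1.2, 7.2.1.4 and Table 2 footnote a). The SAP's windows for those visits run from Screening and are not anchored to the injection or the operation.

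**Working it through.** The documents give no coverage figure to reproduce, so this is a count of days followed by a reading of the rules.

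**1. Coverage from Sun-Start to week 61**

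- The first follow-up window is "6 weeks (± 7 days) after Sun-Start Visit", i.e. days 35 to 49, or 15 days inclusive.
- The last is "60 weeks (± 7 days) after Sun-Start Visit", i.e. days 413 to 427.
- There are six such windows (weeks 6, 12, 24, 36, 48, 60): 6 × 15 = 90 days.
- The period is 61 × 7 = 427 days.
- Uncovered: 427 − 90 = 337 days; 337/427 = 78.9%.
- The gaps before each window in turn are 34, 27, 69, 69, 69 and 69 days, which sum to 337.

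**2. Other conventions**

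- Stopping at week 60: 83 of 420 days covered, 80.2% uncovered.
- Counting each window as 14 days: 84 of 427 covered, 80.3% uncovered.
- Sunitinib runs longer than week 61 for most start dates (Protocol 9.3: "Treatment will continue until End-of-Study", which is 78 ± 2 weeks after Screening). Adding the End-of-Study window, with Sun-Start varied from day 35 to day 118 after Screening, gives 74-79% uncovered.
- Also counting any part of the Sun-Start window ("Five (5) to eight (8) weeks after Nephrectomy Visit") that falls after sunitinib has begun gives about 70-79%. The lowest case is nephrectomy on day 62, Sun-Start on day 97 and End-of-Study on day 560. Covered days are 90 + 29 + 21 = 140 of 463, so 323/463 = 69.8% is uncovered.

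**3. What happens to an extra-visit value**

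| Planned visit it would go to | Position of the value | Nearest-visit sentence | Within-window sentence |
|---|---|---|---|
| Already has a value | Anywhere | Not used | Not used |
| Empty | Inside a window | Used | Used |
| Empty | Between windows | Used | Not used |

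The two sentences disagree only in the last row. The first row does not depend on the windows. The last-observation rule in SAP 6.3.2 could keep an extra-visit value only if it were the patient's last.

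**4. The adverse event route**

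Protocol 11.2 makes an asymptomatic laboratory or vital-sign abnormality an adverse event if it is clinically significant, meets a seriousness criterion or leads to discontinuation. Protocol 10.5.3 does the same for clinically significant examination findings. These reach tables that have no visit windows (SAP 6.3.10). But Protocol 11.2 also discourages double reporting: when an abnormal value comes with symptoms, the symptom is the event and the value is supporting information. Symptoms are the reason for an extra visit.

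**5. Early windows (illustrative dates)**

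- Control patient, nephrectomy on day 25, extra visit on day 40. Day 40 is within 63 days of Screening. It is 15 days after the operation and at least 20 days before Sun-Start (25 + 35 = day 60 at the earliest). If the nephrectomy sample is missing, a post-operative value fills that slot.
- Intuvax patient, Vacc1 on day 5, Vacc2 on day 19, extra visit on day 9. Day 9 lies in the Vacc1 window and is nearer to Vacc1 (4 days) than to Vacc2 (10 days). If the Vacc1 sample is missing, a post-injection value fills it.

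**The case against.** The strongest reply is that symptomatic and clinically significant results already reach tables as adverse events, with abnormal values flagged in listings (SAP 6.3.11; listing 14.3.4.1). That stands for the adverse event and serious adverse event tables. A reader might infer that symptom-driven results vanish from the safety reporting altogether; the documents do not support that. What remains is the abnormal value that accompanies a symptom: it need not become an event itself and may appear in no table.

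A second reply is that the coverage figure does not measure loss. This is right. If scheduled visits are complete, extra-visit values go unused whatever the windows, so contiguous windows alone would recover little. A reader might also infer that about four in five extra visits cannot be allocated. That assumes visits spread evenly over time, which nothing in the documents supports. In the first 13 weeks the windows cover 30 of 91 days, leaving 61/91 = 67%. Patients with progression also leave the visit schedule (Protocol 7.2.1.6).

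Third, exclusion between windows is only one reading, since the nearest-visit sentence would place such a value in an empty slot. That stands, and it is why the two sentences need reconciling.

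Fourth, mislabelling needs a missing pre-procedure value, and Protocol 10.5.5 requires several results before vaccination and nephrectomy. For those parameters it should be rare. An overlap of SFU[60W] with End-of-Study might also be suspected, but Protocol 7.2.1.6 largely settles it by treating a 60-week visit at week 76 or later as End-of-Study.

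Finally, by-visit tables restricted to scheduled visits avoid symptom-triggered sampling, which could differ between arms in an open-label trial. That is a reason to keep them, not a reason to have no summary of the other values.

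**Conclusion.** The point holds for the by-visit laboratory and examination abnormality counts and shift tables, and for the by-visit vital-sign summaries. As written, the plan leaves an extra-visit value out of these whenever the planned visit is filled. On the within-window reading it also leaves out any value between windows. The windows leave 79% of the days from Sun-Start to week 61 uncovered, or roughly 70-80% across the conventions tried. This is a share of calendar time, not of extra visits or abnormal values; the documents give no basis for estimating either of those.

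The mislabelling of post-procedure values is a second, smaller defect, conditional on a missing pre-procedure sample. The survival endpoints, adverse event tables and listings are not affected. The change should be made, because it is cheap and could alter the reported laboratory, vital-sign and examination results.

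**What to change.** 1. For each laboratory, vital-sign and examination parameter, add a summary or shift table of each patient's worst post-baseline value by treatment group, using all scheduled and unscheduled values. Split it by period: before surgery, surgery to Sun-Start, and on sunitinib. This is the change that recovers the omitted values.
2. In SAP 6.6, reconcile the two allocation sentences by replacing the list with contiguous, non-overlapping analysis windows. Cut them at the actual dates of Vacc1, Vacc2, nephrectomy and first sunitinib dose, so that no post-procedure value is labelled pre-procedure.

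The cost is SAP wording and a few extra tables from data already collected. Reported abnormality rates may rise slightly. Worst-value tables will reflect any difference between arms in how often extra visits occur, so they should supplement the by-visit tables and not replace them.
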